Preliminary studies show that signal separation can be detected within as few as 50 signals of 25 positive and 25 negative for training. A maturation process of pattern recognition occurs with 200 signals, 100 positive and 100 negative respectively. This is an initial pilot which can be expanded to the scale of a full study pending promising results. As we will be collecting positive and negative signals from the same patients, we anticipate subject numbers half that of the required signal training numbers.

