#### **Subject Information** – charts, records, images, or specimens are considered ‘subjects’

*Target accrual is the proposed number of subjects to be included in your study at your site. “Subjects” may include Mayo Clinic charts, records, or specimens, and/or charts, records, or specimens received at Mayo Clinic from external sources for collaborating analysis by the investigator under this IRB application:*

Target accrual: 1000 patients

Subject population: Any outpatient adult individual undergoing elective upper endoscopy who consents to study participation

Inclusion Criteria:

1. English speaking
2. Adult (18+) patient undergoing scheduled elective outpatient upper endoscopy
3. Willing and able to consent to research protocol
4. Fasting as required per routine instruction for endoscopy or non- fasting adults accompanying the patient who are able to provide informed consent
5. Able to breath for approximately 5 minutes pre procedure into the Aeonose device with a nose-plug on

Exclusion Criteria:

1. Non-fasting per protocol, or known to have had food or drink outside of routine protocol
2. Non-English speaking
3. < 18 years of age
4. Unable or unwilling to consent to research protocol
5. Inability to tolerate Aeonose breathing (such as those with claustrophobia, anxiety, nasal trauma, etc.)
6. Use of antibiotics or systemic immunosuppressants within three months prior to the date of endoscopy (intranasal and inhaled steroids are allowed)
7. Any prior chemotherapy for esophageal cancer
8. History of squamous cell carcinoma
9. History of gastric or esophageal surgery
10. Per PI discretion, any current medical problem that could alter intended study data collection.

Yes  No Will a Certificate of Confidentiality (COC) be obtained from NIH? If yes,

Who is obtaining the COC: Mayo Clinic investigator, study sponsor, other:

Explain why a COC is needed:

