## Study Design

Methods: *Describe, in detail, the research activities that will be conducted under this protocol:*

Fasting individuals undergoing upper endoscopy in the gastroenterology unit or non-fasting adults accompanying the patients will be enrolled for participation in Aeonose pre-procedural breath testing. These include elective inpatient procedures which have high risk of gastric content retention, but also have increased health risks due to active comorbidities.

Individuals consenting to participation of this study will be asked to provide a breath analysis using the Aeonose per standard acquisition protocol which spans 5 minutes of which the individuals breaths normally through a sterile disposable mouthpiece with sterile disposable air filters for 5 minutes during signal acquisition while wearing a nose plug. This may be completed prior to their endoscopic procedure.

The signals generated from each subject consist of a de-identified electronic breath-print will be analyzed by the investigators and the aggregate results matched using pattern recognition techniques to localize into fasting and non-fasting states. For the pilot portion of this study, the primary outcome is to establish separation of these signals in the initial cohort.

**Resources:** *Describe the available resources to conduct the research (personnel, time, facilities, mentor commitment, etc.):*

The lab group and study team consists of a full time laboratory researcher, gastroenterology clinical investigator fellows, and clinical research coordinators to support the study. The lab is based in the Alfred Main laboratory space. The lab group has already received on-site training by the eNose Company in the operation of the Aeonose. One Aeonose unit is immediately available for dedicated use towards this project and a sufficient supply of disposables (filters and mouthpieces) is already in stock for this project. The eNose Company who is a collaborating partner has dedicated further resources (more Aeonose units and disposables) as needed.

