### Statistical Considerations

**Power Statement:** This initial portion of the study is a pilot/feasibility study with 25 subjects. Based on the experience of the eNose company who will be providing analytical and statistical support in pattern recognition a minimum of 25 positive and 25 negative samples are needed to start to discern separation. In other models, 100 positive and 100 negative training set is needed to create a robust diagnostic model. Further subjects beyond that, such as in multiple sites further fine tune the diagnostic model through pattern recognition learning algorithms (artificial neural networks).

Sample size calculations using 80% power with a 5% level of significance, assuming a 50% fasting / non-fasting prevalence, with a test with a minimum sensitivity and specificity of 80% suggests that about 450 patients are required to achieve statistical power. We will obtain 200 fasting and 200 non-fasting individuals to achieve aim for an accuracy greater than 85%. An additional blinded test group of 50 fasting and 50 non-fasting subjects will be used for model validation. Statistical modeling for training and validation will be performed by the eNose Company using artificial neural networks for pattern recognition as they have been already providing this support through our research collaboration. We will perform descriptive statistics of patient demographics and characteristics

**Data Analysis Plan:** The eNose company has proprietary expertise in digital signal processing, artificial neural network pattern recognition techniques, the basis which is on published algorithms and established methodologies. The eNose company in collaboration with the investigators will receive encrypted, de-identified digital signatures for training and create a diagnostic model. If the pilot study proves fruitful, this protocol will be expanded into a full study by increasing the enrollment to a full study.

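### Eligibility admits outpatients only, but Methods also enrol elective inpatients, who as the classes are defined could enter only the fasting class

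*Combined protocol and SAP*

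**What the plan says.** **Setting.** Under Subject Information, the subject population is "Any outpatient adult individual undergoing elective upper endoscopy who consents to study participation", and inclusion criterion 2 is "Adult (18+) patient undergoing scheduled elective outpatient upper endoscopy". The Methods paragraph of Study Design opens with who will be enrolled and continues: "These include elective inpatient procedures which have high risk of gastric content retention, but also have increased health risks due to active comorbidities".

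**Classes.** Inclusion criterion 4 reads "Fasting as required per routine instruction for endoscopy or non- fasting adults accompanying the patient who are able to provide informed consent". Methods agree: "Fasting individuals undergoing upper endoscopy in the gastroenterology unit or non-fasting adults accompanying the patients will be enrolled". Exclusion criterion 1 is "Non-fasting per protocol, or known to have had food or drink outside of routine protocol"; it has to be read as applying to patients, since otherwise it would bar the companions too. The background text in Purpose differs: "As we will be collecting positive and negative signals from the same patients, we anticipate subject numbers half that of the required signal training numbers". Statistical Considerations plans 200 fasting and 200 non-fasting individuals for the model, with an accuracy target above 85%, and a further 50 and 50 as a blinded test group. These counts fit two separate groups.

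**Related provisions.** Exclusion 6 bars recent antibiotics and systemic immunosuppressants. Exclusion 10 lets the investigator exclude medical problems that could affect data collection. Patients' charts are reviewed for medication, disease and other breath modifiers. The secondary endpoint concerns influencing factors. No matching, adjustment or stratification by setting is described.

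**The concern.** The eligible population is not settled. Whoever follows Methods enrols patients who are ineligible under criterion 2; whoever follows criterion 2 does not do what Methods describe. The accuracy estimate then has no defined population.

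The contradiction also reaches the primary comparison. If inpatients enter, they enter on one side only. An artificial neural network can use any signal that separates the classes, including disease and medication. A blinded test group recruited in the same way would share the imbalance and would not expose it.

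Finally, the fasting label rests on compliance with routine instruction, while Methods attribute a high risk of retained gastric contents to these inpatients. Some could carry the fasting label with food in the stomach, which is the state that Purpose sets out to detect.

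**Working it through.** **1. The plan's own figure.** Statistical Considerations gives about 450 patients from 80% power, a 5% level, 50% prevalence and minimum sensitivity and specificity of 80%. No comparison value, precision or sidedness is given, so it cannot be reproduced uniquely. With n = [z(α)√(p0(1−p0)) + z(0.8)√(p1(1−p1))]² / (p1−p0)²:
- One-sided, 0.75 against 0.80: (1.645×0.433 + 0.842×0.400)² / 0.05² gives 441.
- Two-sided, 0.80 against 0.85: (1.960×0.400 + 0.842×0.357)² / 0.05² gives 471. The arcsine version of this comparison gives 452.

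Nothing below depends on this figure.

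**2. Setting, side by side.** Subject population: outpatient. Criterion 2: outpatient. Methods: elective inpatient procedures included. No other section resolves the difference.

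**3. Which class an inpatient can enter.** By criterion 4 and Methods, a person having endoscopy is enrolled as fasting, and exclusion 1 bars a non-fasting patient. Non-fasting subjects are accompanying adults. An inpatient having endoscopy can therefore enter only the fasting class. This fails only if the same-patient statement in Purpose governs, in which case each patient would be in both classes.

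**4. Scale, inpatient status alone.** The inpatient share f of the fasting class is not stated, so it is varied here as an assumption. Take a classifier that detects inpatient status perfectly and knows nothing about fasting. It classifies a share f of the fasting class and all of the non-fasting class correctly. With equal classes, accuracy = 0.5×f + 0.5×1 = 0.5 + f/2.

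| f | Inpatients among 200 / 50 fasting | Accuracy |
|---|---|---|
| 0% | 0 / 0 | 50% (chance) |
| 10% | 20 / 5 | 55% |
| 20% | 40 / 10 | 60% |
| 50% | 100 / 25 | 75% |
| 70% | 140 / 35 | 85% |

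**5. Scale, a partly informative test.** Let s be the proportion of fasting outpatients classified correctly and r the proportion of fasting inpatients. The fasting class as a whole reads (1−f)s + f r, a shift of f(r−s). Assume s = 75%:
- r = 100%: f = 20% gives 0.8×0.75 + 0.2×1.00 = 80%; f = 40% gives 0.6×0.75 + 0.4×1.00 = 85%.
- r = 85%: f = 20% gives 0.8×0.75 + 0.2×0.85 = 77%; f = 40% gives 0.6×0.75 + 0.4×0.85 = 79%.
- r = 75%: no shift.
- r below 75%: the shift is downwards. This could happen if the test responds to retained food in patients labelled fasting.

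With equal classes, overall accuracy moves by half the shift: 5 points in the fasting class is 2.5 points of accuracy. None of f, s or r is in the documents, so these figures show what the answer depends on and do not estimate the bias.

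**The case against.** The strongest case on the other side accepts the contradiction and disputes its consequences.

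- **Inpatients do not create the confounding.** With outpatients alone, patients are already compared with companions. This stands. A reader might infer that admitting inpatients turns the contrast into ill versus well; the documents do not say that companions are well and give no inpatient share, so that is not shown.
- **Entry to the fasting class only is not certain.** The same-patient statement in Purpose would put each patient in both classes. This stands as a qualification. Criterion 4, Methods and the separate counts in Statistical Considerations all point to two groups.
- **Label error is not specific to inpatients.** Purpose says that food can be retained despite standard fasting, so outpatients are affected too. If fasting means only compliance with instruction, a compliant inpatient with retained food is not mislabelled. This stands in part: the reference state is unclear across the study, and inpatients would add to the problem. A reader might infer that the plan calls retained food likely in inpatients, or picked them for that reason; it states a high risk and gives no reason for selection.
- **Safeguards exist.** Exclusions 6 and 10, chart review and the secondary endpoint all bear on breath modifiers. None bars inpatients, and none protects the primary contrast. Exclusion 10 is discretionary and sits awkwardly beside a sentence that brings in patients with active comorbidities.
- **The scale figures are illustrative.** This stands fully. They reach 80% and 85% only at perfect recognition, and the 85% in the plan is an accuracy target, not a rate for one class.

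**Conclusion.** The contradiction on setting is certain: it lies in current text and nothing resolves it. As the classes are defined in the eligibility criteria and Methods, inpatients would add comorbidity, and possibly label error, to the fasting class only. That conclusion assumes that exclusion 1 applies to patients and that the two-group design governs rather than the same-patient statement.

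The size of any bias cannot be estimated without the inpatient share and the test's behaviour in inpatients, and its direction is open as well. It would be wrong to conclude that inpatients would carry the study past 80% or 85%: by inpatient status alone, the accuracy target needs about 70% of the fasting class to be inpatients. What can be said is that the plan does not define the population to which its accuracy estimate applies, and that this should be settled before enrolment continues.

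**What to change.** Reconcile Methods with Subject Information in one of two ways; the choice is the sponsor's.

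1. Delete the inpatient sentence from Methods, so that it agrees with the outpatient population and criterion 2.
2. Amend the subject population and criterion 2 to admit inpatients, record the setting for each subject, and report accuracy separately for inpatients and outpatients, so that the primary estimate applies to the stated outpatient population. The plan should also say whether inpatients contribute to training. Under the two-group design there is no inpatient non-fasting group, so the inpatient results could show only the proportion of fasting inpatients classified correctly.

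Under either option, reconcile the same-patient statement in Purpose with criterion 4, Methods and the class counts.

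The cost is a wording modification to the protocol; the second option adds one recorded variable and one stratum in the report. Either reduces the patient-versus-companion confounding but does not remove it, and that needs its own answer in the design.

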### Purpose

Hypothesis: An electronic nose can discern breath profiles between fasting and non-fasting individuals

Aims, purpose, or objectives: In patients undergoing endoscopic procedures, there currently is not a non-invasive process to assess whether the patient presents in a fasting state which is required for moderate sedation or anesthesia-assisted endoscopy. With the increased prevalence of type 2 diabetes and its associated comorbidity of gastroparesis which causes delayed gastric emptying, this may present retained food in the stomach even in individuals who comply to standard fasting protocols.

In non-fasting individuals, the risk of a sedation related complication such as aspiration increases and often the procedure must be aborted and repeated on another day following more prolonged fasting and medication administration. This adds to increased cost and delay to patient care.

We propose a mechanism by which we can quickly screen and assess for fasting and non-fasting states in individuals scheduled for routine endoscopy by utilizing a non-invasive breath analyzer called an electronic nose by which through pattern recognition we analyze electronic changes in exhaled volatile organic compounds interfacing with an electronic sensor that creates an electronic signature, or smell-print that distinguishes the fasting and non-fasting states.

Background (*Include relevant experience, gaps in current knowledge, preliminary data, etc.*): We eNose Company (eNose B.V., Zupten, NL), who will supply the electronic nose apparatus called the Aeonose device. This is a handheld, portable battery operated unit with a built in sensor that allows for data collection at the point of care with the subject breathing directly into the apparatus. The technology which is based on the prior commercially available Diagnose which was CE marked, and the Aeonose has already been utilized in large studies in breath analysis for head and neck cancer screening, tuberculosis screening, and is nearing commercialization by the eNose Company.

We have demonstrated experience working with the eNose Company in our study Identification of *C. difficile* infected stool by electronic nose using a device (Aetholab) with the same sensor technology (14-001369).

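### Time since last food or drink before the breath is neither set nor recorded in the protocol, so residue in the mouth may contribute to the separation of non-fasting companions from fasted patients

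*Combined protocol and SAP*

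**What the plan says.** Study Design names the two classes: "Fasting individuals undergoing upper endoscopy in the gastroenterology unit or non-fasting adults accompanying the patients will be enrolled". Inclusion criterion 4 under Subject Information agrees, admitting those "Fasting as required per routine instruction for endoscopy or non- fasting adults accompanying the patient who are able to provide informed consent".

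Sampling is the same for everyone. Participants "provide a breath analysis using the Aeonose per standard acquisition protocol which spans 5 minutes", and each of them "breaths normally through a sterile disposable mouthpiece with sterile disposable air filters for 5 minutes during signal acquisition while wearing a nose plug". Beyond mouthpiece, filters, nose plug and duration, the contents of that standard procedure are not given.

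The motivating problem under Purpose is delayed gastric emptying: "this may present retained food in the stomach even in individuals who comply to standard fasting protocols".

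Statistical Considerations plans 200 fasting and 200 non-fasting individuals, with an aim of accuracy above 85%, and adds: "An additional blinded test group of 50 fasting and 50 non-fasting subjects will be used for model validation".

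Two other places come near the point. Review of Chart, Images, Specimens provides for looking up breath-modifying factors in the patient's chart. Endpoints has a secondary endpoint on factors that influence the breath analysis, with no factor named.

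**The concern.** Breath is collected through the mouth. For food and drink, the classes differ in recent oral exposure by definition: patients have fasted as instructed, and companions have not. A companion could be tested minutes after a meal or a coffee. Such a person is correctly labelled non-fasting, so this is not a labelling error. The question is where the signal comes from.

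The planned neural network learns whatever separates the labelled signals. If residue in the mouth helps, it will be used. The resulting accuracy would then say less than it appears to about a compliant patient with food still in the stomach, who has taken nothing recently and lacks the oral cue.

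If the time of last intake is not written down at sampling, it cannot be recovered. The chart review is worded for the patient's chart and would not show what a companion ate or drank that morning.

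**Working it through.** **Does the protocol control or record recent intake?** I checked each place where it could.

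- Study Design: equipment and duration only, plus the cited acquisition procedure, whose contents are not reproduced.
- Exclusion 1: concerns food or drink outside the fasting instruction. It sets no interval for a non-fasting companion and, read literally, would exclude that person.
- Exclusion 10: investigator discretion, limited to current medical problems.
- Chart review: patients' charts, so no record of a companion's recent intake.
- Secondary endpoint: general, and it cannot use a factor that was not recorded.

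No section states or records time since last intake.

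**The plan's own figures.** The plan does not derive the 85% aim, so there is nothing to reproduce there. Its one calculated figure, about 450 patients, can be approached with a two-sided arcsine test of 0.80 against 0.85 at 80% power and 5% significance, which gives 452. That pairing is my reading, since the plan names no formula. The figure does not bear on this point.

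**How large could the effect be?** Take a model that reacts only to mouth residue and has no stomach signal. Let q be the share of companions with detectable residue, d the probability that the model detects residue, and f its false-alarm rate when there is none. Assume fasted patients have none. All three values are assumptions; the documents give none of them. Only the 1:1 class ratio and the 85% aim come from the plan.

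- Sensitivity = qd + (1 − q)f
- Specificity = 1 − f
- Accuracy at 1:1 = (sensitivity + specificity)/2 = [1 + q(d − f)]/2
- Setting accuracy to 0.85 gives q = 0.70/(d − f)

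With d = 0.95 and f = 0.05, accuracy is:

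- q = 0.6: (1 + 0.6 × 0.90)/2 = 77.0%
- q = 0.8: (1 + 0.8 × 0.90)/2 = 86.0%
- q = 0.9: (1 + 0.9 × 0.90)/2 = 90.5%

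Share of companions with residue needed for 85% accuracy:

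| d | f | q needed |
|---|---|---|
| 1.00 | 0 | 0.70/1.00 = 70% |
| 0.95 | 0.05 | 0.70/0.90 = 78% |
| 0.90 | 0.10 | 0.70/0.80 = 87.5% |
| 0.85 | 0.15 | 0.70/0.70 = 100% |

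At the 78% threshold (d = 0.95, f = 0.05), sensitivity is 0.778 × 0.95 + 0.222 × 0.05 = 75% and specificity is 95%. The 80% minimum sensitivity used in the sample-size statement would need q = (0.80 − 0.05)/0.90 = 83%.

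For a fasted patient with food in the stomach and a clean mouth, this model's sensitivity equals f: 5% in the main illustration, 0% to 15% across the table. That follows directly from assuming no stomach signal.

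**Would the blinded group reveal it?** Its classes are again fasting and non-fasting, with no stated change in sampling. The number correct is the sum of Binomial(50, sensitivity) and Binomial(50, specificity). With d = 0.95 and f = 0.05, the chance of more than 85 correct out of 100 is 14% at q = 0.7, 57% at q = 0.8 and 95% at q = 0.9. A pass would not distinguish this model from one with a gastric signal.

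**The case against.** The strongest reply is that the breath is taken under a standard acquisition procedure that is cited but not reproduced, by a team trained on site by the manufacturer. That procedure may already cover mouth preparation. This stands. A reader might infer that no pre-breath control exists; the documents support only that none is stated here.

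A second reply is that the hypothesis and the primary endpoint concern fasting against non-fasting state, not stomach contents as such. A trace in the mouth of someone who has just eaten is not plainly a wrong signal for that endpoint. This also stands. The concern therefore bites on the retained-food case under Purpose, which is one motivation among others.

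Third, a reader might extend the argument to gum and tobacco as differences between the classes. The content of the fasting instruction is not given, and exclusion 1 mentions only food and drink, so such a difference is not documented. Recording them is reasonable; asserting a class difference is not.

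Fourth, the chart review and the secondary endpoint partly anticipate influencing factors. They do so only in general terms, and neither provides for recording recent intake, so this reply does not remove the gap.

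Finally, the Background says both signal types will come from each patient, which conflicts with the companion design. That needs resolving, but a fed sample from the same person could carry mouth residue too.

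**Conclusion.** The point holds as a possibility that the plan neither limits nor allows anyone to examine. Oral exposure to food and drink differs between the classes by construction, time since intake is not recorded, and the blinded group shares the same structure.

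Its size is unknown. Under the assumed values, mouth residue alone reaches 85% accuracy only if about 78% of companions carry it, with a range of 70% to 100%. Below those shares residue could still inflate accuracy, but it would not by itself give an expected accuracy at the aim. A reader might infer that the model is likely to meet its target on mouth odour alone, or that it would miss nearly all patients with retained food. The documents support neither: they do not say when companions last ate, how detectable residue is, or whether a stomach signal is absent.

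This is worth correcting before enrolment because the missing information cannot be recovered later. It is not grounds to reject the design.

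**What to change.** In Study Design:

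- State the pre-breath condition, or confirm that the cited acquisition protocol sets one and say what it is.
- Apply the same minimum interval since oral intake to both classes, with its length set by the investigators. The unit's fasting instruction is not touched.
- For every subject, record at sampling the time and type of last oral intake, including gum and tobacco.

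Under the secondary endpoint, report sensitivity in the non-fasting class by time since last intake. This shows whether accuracy is confined to very recent intake. It does not by itself separate a mouth signal from a stomach signal, because both change with time after eating, and the report should say so.

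Reconcile the Background statement that both signals come from each patient, and exclusion 1, with the companion design in inclusion criterion 4 and Study Design.

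The cost is a short wait for some companions, one extra field on the form, and possibly a lower headline accuracy if mouth residue was contributing.

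### Breath-test timing relative to endoscopy is stated inconsistently, and the paired-signal assumption leaves a patient's own fed breath no same-day slot before the procedure

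*Combined protocol and SAP*

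**What the plan says.** All references are to the combined protocol and SAP.

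**Timing of the breath test**
- Study Design, Methods, on when the test is done: "This may be completed prior to their endoscopic procedure".
- Study Design, opening sentence of the Methods: participants "will be enrolled for participation in Aeonose pre-procedural breath testing".
- Subject Information, inclusion criterion 5: "Able to breath for approximately 5 minutes pre procedure into the Aeonose device with a nose-plug on".

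**Who gives the fed signal**
- Purpose, end of the background: "As we will be collecting positive and negative signals from the same patients, we anticipate subject numbers half that of the required signal training numbers".
- Statistical Considerations, Power Statement: a pilot of 25 subjects, with at least 25 positive and 25 negative samples needed.
- Study Design, Methods: "non-fasting adults accompanying the patients will be enrolled". Inclusion criterion 4 also admits such companions.
- Statistical Considerations, Power Statement: for the larger study, 200 fasting and 200 non-fasting individuals, plus a blinded test group of 50 and 50.

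**State of the patient before endoscopy**
- Inclusion criterion 4 has patients fasting as routinely instructed, and exclusion criterion 1 removes anyone "Non-fasting per protocol, or known to have had food or drink outside of routine protocol".
- Purpose describes "a fasting state which is required for moderate sedation or anesthesia-assisted endoscopy".

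No section describes a second visit, a second breath or a breath after the procedure. None prohibits a later breath or asks for the time of the breath relative to sedation or endoscopy.

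**The concern.** The device reads a pattern in exhaled volatile compounds, and a neural network sorts the patterns into two classes. Such a network will use any feature that differs between the classes. If breaths with one label tend to be taken after sedation and endoscopy and breaths with the other label before, it can learn procedure status instead of stomach state.

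Three features of the plan leave that possibility open: a permissive timing sentence, a paired-signal assumption with no pre-procedure place for the fed half of the pair, and no record of timing from which late breaths could be identified afterwards.

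The primary endpoint is the ability to tell fasting from non-fasting breath, and the pilot outcome is simply separation of the signals. A separation produced by the procedure would count as success and support expansion to the full study. The blinded test group would not reveal the problem if collected under the same timing rule. The intended use is screening before sedation, where the misleading cue is absent, so performance would not carry over.

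**Working it through.** **Step 1: does the pilot size depend on pairing?**
Inputs (Power Statement and Purpose): 25 positive + 25 negative = 50 signals; 25 subjects; subject numbers half the signal numbers.
- Two signals per subject: 50 / 2 = 25 subjects, which reproduces the stated pilot size exactly.
- One signal per subject: 50 / 1 = 50 subjects.

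The stated pilot therefore fits the same-patient assumption and does not fit a design with one signal per person.

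**Step 2: where can a patient's own fed breath be taken?**

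| Possible slot | What the documents say |
|---|---|
| Same day, before endoscopy | Closed to patients by inclusion 4 and exclusion 1 |
| Same day, after endoscopy | Not described, not barred; the timing sentence is permissive |
| Another day | Not described, not barred |

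The paired assumption can be met only in a slot that the protocol does not describe. One of the two remaining slots follows sedation and the procedure.

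**Step 3: what would post-procedure fed breaths do to apparent accuracy?**
This is an illustration; f is not in the documents. Assume:
- a share f of fed-labelled breaths is taken after the procedure;
- all fasting breaths are taken before it;
- the groups are equal in size;
- the sensor detects procedure or sedation effects perfectly and carries no information on stomach state.

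A classifier that calls every post-procedure breath fed has sensitivity f for the fed state and specificity 1. Accuracy = 0.5 × f + 0.5 × 1 = (1 + f)/2.

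| f | Apparent accuracy |
|---|---|
| 0 (companions only) | 50% |
| 0.25 | 62.5% |
| 0.50 | 75% |
| 0.70 | 85% |
| 1 | 100% |

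The Power Statement aims for accuracy above 85%. Solving (1 + f)/2 = 0.85 gives f = 2 × 0.85 − 1 = 0.70, so any f above 0.70 would exceed the target with no fasting information.

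**Step 4: the companion design.**
Companions enter the study as people accompanying a patient, with no endoscopy or sedation described for them, so f = 0. Timing can then be tied to the label only if some patients breathe late, which would put procedure effects into the fasting class alone. If every patient breathes before the procedure, as inclusion 5 and the opening of the Methods indicate, this source of bias is absent.

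**The case against.** The strongest reply is that the protocol, read as a whole, intends pre-procedure testing. The enrolment sentence and inclusion 5 both say so, and the stated purpose is screening before sedation. The permissive verb may simply allow for companions, who have no procedure to precede. The Methods ask each person for one breath analysis, and the operative text takes fed signals from companions. The same-patient sentence appears only in the background.

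Much of this stands, and it rules out three stronger readings that a reader might infer:

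- *That pre-procedure timing is merely optional throughout.* Two other statements describe the test as pre-procedure. The fault is inconsistency.
- *That the protocol plans fed breaths after sedation.* No section does. A fed breath on another day is equally undescribed, and nothing confines collection to one visit.
- *That fed status and post-sedation status coincide, so 100% accuracy is to be expected without fasting information.* This needs paired signals, same-visit collection, the fed breath after the procedure in every case, and a sensor that detects procedure effects. The documents support only the first, and the enrolment text contradicts even that. With companions as the fed group, the label cannot coincide with sedation.

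The reply does not remove the point. Inclusion 5 states an ability, not a sampling rule. The timing sentence refers to participants' own endoscopic procedure, so it leaves patient timing open whatever it means for companions. The pilot size cannot be dismissed as background, because it matches the paired assumption exactly.

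**Conclusion.** The concern holds in a limited form. The documents give the timing of the breath test two ways and the source of the fed signal two ways. Together these permit, but do not plan, a fed breath taken from a patient after endoscopy and sedation. The possible bias in the primary endpoint runs from none (fed breaths from companions, all patient breaths before the procedure) up to apparent accuracy of 100% in the extreme case of f = 1, passing the protocol's 85% mark at f = 0.70. These figures rest on an assumed f, equal groups, all fasting breaths taken before the procedure, and a sensor assumed to register procedure effects. They show how far the ambiguity could matter and do not predict what will happen. The point should be corrected before collection, because late breaths could not be identified afterwards unless their timing is recorded.

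**What to change.** 1. In Study Design, Methods, replace the permissive wording so that, for patients, the breath test *must be completed before sedation and the procedure*.
2. Record the time of every patient breath relative to first sedation and to the procedure.
3. State that signals taken after the procedure are not used for training, the pilot outcome or validation.
4. Reconcile Purpose, Subject Information, Study Design and Statistical Considerations on who gives the fed signal and when. If pairing is kept, describe the occasion on which a patient's fed breath is taken. If companions supply it, delete the same-patient sentence and restate the pilot size.

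**Cost.** Items 1 to 3 need protocol wording, a few recorded times and possibly the loss of some late signals. Item 4 costs more. Keeping pairing needs a sampling occasion that the protocol does not yet contain. Dropping it raises the pilot from 25 to 50 subjects. The larger study already counts separate individuals (200 + 200 + 50 + 50 = 500), so even with a separate pilot the total is 500 + 50 = 550, well within the target accrual of 1000.
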